Cover Page:

Title: Evaluation of AI-based Risk Assessment Model in Plastic Surgery

NCT Number: [NCT ID not yet assigned]

Document Date: July 11, 2024

Document Review Statement:

This document was most recently updated and reviewed by the sole researcher, [name], EMBA, on July 11, 2024. As there is no human subjects protection review board required for this study, this date reflects the most recent review and update by the principal investigator.

Study Protocol

Introduction

This study protocol outlines the procedures, objectives, and methodologies for the observational study titled "Evaluation of AI-based Risk Assessment Model in Plastic Surgery." The primary aim is to evaluate the clinical utility of an AI-based risk assessment model in predicting and mitigating complications in patients undergoing elective plastic surgery.

Study Objectives

- To evaluate the effectiveness of the AI-based risk assessment model in predicting surgical complications.
- To determine the correlation between various clinical factors (such as BMI, age, and smoking habits) and the AI-generated risk scores.
- To assess the impact of AI-generated recommendations on surgical outcomes and complication rates.

Study Design

This is an observational study with a prospective time perspective. The study involves the collection of clinical data from patients undergoing elective plastic surgery. The AI model analyzes this data to provide personalized risk scores and recommendations.

Participant Eligibility

Inclusion Criteria:

- Individuals aged 18 and older.
- Scheduled to undergo elective plastic surgery.
- Agreement to follow preoperative and postoperative recommendations provided by [name], according to the AI-based risk assessment model.

Exclusion Criteria:

- Individuals below 18 years of age.
- Patients with a history of severe allergic reactions to anesthesia.
- Those unable to provide informed consent.

Study Population Description

Participants are individuals undergoing elective plastic surgery. They will complete an online form collecting data on various clinical factors, such as age, height, weight, smoking habits, and comorbidities. The system calculates the risk score, body mass index (BMI), and Caprini score.

Data Collection

The following data will be collected from each participant:

- Age
- Height and weight (to calculate BMI)
- Smoking habits
- Comorbidities
- Caprini score (calculated by the system)

- Risk group classification (High, Moderate, Low)

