- Complications (Hematoma, Seroma, Infection, Dehiscence, Necrosis, DVT/PE, ASIA Syndrome)

Study Procedures

Participants will undergo a risk assessment using the AI model, which evaluates multiple risk factors based on their clinical data and patient history. The model will then generate personalized recommendations, which include:

- Weight management guidance for patients with a BMI greater than 25.1.
- Smoking cessation advice for patients who smoke.
- Blood pressure control recommendations for hypertensive patients.
- Doppler ultrasound screening for deep vein thrombosis (DVT) and varices.
- Nutritional consultations for patients with a BMI of 25.1 or lower.
- Specialist referrals based on comorbidities and psychiatric consultations for Body Dysmorphic Disorder (BDD) screening.

Follow-Up

The follow-up period for this study ranges from 2 to 41 months, with a mean follow-up of 15 months. During this time, data on patient outcomes, including complication rates and patient satisfaction, will be collected and analyzed.

Outcome Measures

Primary Outcome Measure

Title: Incidence of complications within 45 days post-surgery

Description: The primary outcome measure is the incidence of complications (such as hematoma, seroma, infection, etc.) occurring within 45 days after elective plastic surgery. Complications are identified and recorded based on clinical follow-up visits and patient reports.

Conclusion

This study protocol provides a comprehensive overview of the study design, objectives, data collection methods, and statistical analysis plan for the observational study "Evaluation of AI-based Risk Assessment Model in Plastic Surgery." The integration of AI-generated recommendations is expected to enhance preoperative planning and postoperative care, ultimately improving patient safety and satisfaction.

Statistical Analysis Plan (SAP)

Introduction

This Statistical Analysis Plan (SAP) outlines the statistical methods and analyses to be performed for the study titled "Evaluation of AI-based Risk Assessment Model in Plastic Surgery." The primary aim of the study is to assess the clinical utility of an AI-based risk assessment model in identifying and mitigating risk factors associated with complications in patients undergoing elective plastic surgery.

Study Objectives

- To evaluate the effectiveness of the AI-based risk assessment model in predicting surgical complications.

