- To determine the correlation between various clinical factors (such as BMI, age, and smoking habits) and the AI-generated risk scores.
- To assess the impact of AI-generated recommendations on surgical outcomes and complication rates.

Study Design

This is an observational study with a prospective time perspective. The study involves the collection of clinical data from patients undergoing elective plastic surgery. The AI model analyzes this data to provide personalized risk scores and recommendations.

Data Collection

The following data will be collected from each participant:

- Age
- Height and weight (to calculate BMI)
- Smoking habits
- Comorbidities
- Caprini score (calculated by the system)
- Risk group classification (High, Moderate, Low)
- Complications (Hematoma, Seroma, Infection, Dehiscence, Necrosis, DVT/PE, ASIA Syndrome)

Primary Outcome Measure

Title: Incidence of complications within 45 days post-surgery

Description: The primary outcome measure is the incidence of complications (such as hematoma, seroma, infection, etc.) occurring within 45 days after elective plastic surgery. Complications are identified and recorded based on clinical follow-up visits and patient reports.

Statistical Methods

The following statistical methods and formulas will be used for data analysis:

Descriptive Statistics:

- Frequency and percentage of patients in each risk group (High, Moderate, Low)
- Incidence of complications in each risk group

- Relative risk and odds ratio for complications in each risk group

Pearson Correlation:

- Correlation between risk factors (Age, BMI, Smoking habits, etc.) and AI-generated risk scores

python

Copiar código

```
stats.pearsonr(corr4['Risk factor'], corr4['BMI'])

stats.pearsonr(corr4['Risk factor'], corr4['Caprini score'])

stats.pearsonr(corr4['Risk factor'], corr4['Age'])

stats.pearsonr(corr4['Risk factor'], corr4['Smoking habit'])

stats.pearsonr(corr4['Risk factor'], corr4['Male'])

stats.pearsonr(corr4['Risk factor'], corr4['Female'])

stats.pearsonr(corr4['Risk factor'], corr4['High blood pressure'])
```

Outcome Analysis:

- Count and percentage of complications in each risk group
- Calculation of relative risk and odds ratio

python

Copiar código

Relative Risk = (Incidence in high-risk group) / (Incidence in low-risk group)

Odds Ratio = (Odds of complications in high-risk group) / (Odds of complications in low-risk group)

Data Analysis

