Data analysis will be performed using Python, and the complete notebook with the analysis code and results is available at the following link: [Colab Notebook](#).

Access Instructions

To request permission to access the individual participant data (IPD) and supporting information, please email [contact]. Detailed instructions for requesting access can be found at [IPD Sharing Instructions](#).

Conclusion

This SAP provides a detailed plan for the statistical analysis of the study "Evaluation of AI-based Risk Assessment Model in Plastic Surgery." The analysis aims to provide insights into the effectiveness of the AI model in predicting and mitigating surgical complications, ultimately improving patient outcomes and safety.

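### Because every participant agrees to follow the model's advice, the High/Low relative risk and odds ratio describe stratification after advice: they do not measure the score's advice-free predictive strength and cannot show mitigation

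*Combined protocol and SAP*

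**What the plan says.** The Study Objectives, identical in the protocol and the SAP, include one on prediction, "To evaluate the effectiveness of the AI-based risk assessment model in predicting surgical complications", and one on effect, "To assess the impact of AI-generated recommendations on surgical outcomes and complication rates".

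The protocol's Inclusion Criteria require "Agreement to follow preoperative and postoperative recommendations provided by [name], according to the AI-based risk assessment model". Under Study Procedures, the risk assessment comes first: "The model will then generate personalized recommendations, which include" six kinds of advice. Some are tied to a single factor, for example "Smoking cessation advice for patients who smoke". Others reach further: nutritional consultation goes to patients at or below the BMI cut-off, and Doppler screening is listed without restriction.

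The SAP's Statistical Methods plan counts, percentages and incidence of complications in each risk group. They add the ratio "Relative Risk = (Incidence in high-risk group) / (Incidence in low-risk group)" and an odds ratio for the same two groups. The Pearson correlations relate patient factors to the score, not to complications. Neither Data Collection list has a field for whether recommendations were followed. The SAP's Conclusion states: "The analysis aims to provide insights into the effectiveness of the AI model in predicting and mitigating surgical complications".

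**The concern.** The outcome is measured after an intervention that the model itself generates and that all participants have agreed to accept. The plan then compares complications between the model's own risk groups. That contrast carries two things at once: how well the score separated patients before advice, and how far the advice changed risk in each group. Nothing else in the plan pulls them apart. There is no unexposed, historical or concurrent comparator, and adherence is not recorded.

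This goes beyond the lack of a comparator for the mitigation objective. Even if the mitigation claim were dropped, the ratio could still be misread as the score's own predictive strength. At stake is the primary aim, which joins prediction and mitigation, and the closing claim of the SAP, which repeats both.

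**Working it through.** **Inputs.** The documents give no sample size, complication rate or expected ratio, so there is no planned figure to reproduce. From the documents: universal agreement to advice (Inclusion Criteria), assessment before advice (Study Procedures), and High/Low ratios as the between-group contrast (Outcome Analysis). All risks and reductions below are assumptions.

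**Formula.** Let pH and pL be the 45-day risks without advice, RR0 = pH/pL, and eH and eL the relative reductions due to advice. Then

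observed RR = pH(1 − eH) / [pL(1 − eL)] = RR0 × (1 − eH)/(1 − eL).

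The observed ratio falls below RR0 if eH > eL, equals it if eH = eL, and exceeds it if eH < eL.

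**Main case, pH = 20%, pL = 5%.**

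| Reduction High / Low | Observed High | Observed Low | RR | OR |
|---|---|---|---|---|
| 0% / 0% | 20% | 5% | 4.00 | 4.75 |
| 25% / 0% | 15% | 5% | 3.00 | 3.35 |
| 50% / 0% | 10% | 5% | 2.00 | 2.11 |
| 75% / 0% | 5% | 5% | 1.00 | 1.00 |
| 50% / 25% | 10% | 3.75% | 2.67 | 2.85 |
| 50% / 50% | 10% | 2.5% | 4.00 | 4.33 |
| 25% / 50% | 15% | 2.5% | 6.00 | 6.88 |

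**Other starting risks, RR only.**

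| No-advice risks | RR0 | 50% / 0% | 50% / 50% | 25% / 50% |
|---|---|---|---|---|
| 30% vs 10% | 3.00 | 1.50 | 3.00 | 4.50 |
| 10% vs 4% | 2.50 | 1.25 | 2.50 | 3.75 |

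**Two explanations for one result.** An observed 10% against 5% (RR 2.0) fits no-advice risks of 20% and 5% with advice that halves risk in High. It fits equally well no-advice risks of 10% and 5% with advice that does nothing.

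**Per-group incidence.** In the 50% / 50% row, complications are halved in both groups. The plan would report 10% and 2.5% with nothing to compare them with, so the benefit would show in neither the ratio nor the incidences.

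**The case against.** A reader might infer that the ratio must shrink as the advice succeeds, so that one statistic sends opposite signals on prediction and mitigation. The documents do not support that. Study Procedures tie advice to individual factors rather than to the score or risk group. The two BMI items together cover every patient, so Low-group patients also receive an intervention. Shrinkage needs a larger relative reduction in High than in Low. That is plausible, because weight, smoking and blood-pressure advice target factors that the SAP correlates with the score, but it is not assured.

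A reader might also infer that no value of the ratio says anything about prediction. That too goes too far. If advice works at least as well in High as in Low, the observed ratio is at or below RR0, and a value well above 1 supports prediction conservatively. The protection is lost only if advice works better in Low. With reductions of 25% and 50% the multiplier is 0.75/0.50 = 1.5, so a score with no separation at all would show a ratio of 1.5.

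Three further points stand. Per-group incidence is planned alongside the ratios. The SAP nowhere assigns the ratios to the third objective. Several recommendations that were due can be derived from the BMI, smoking and comorbidity fields, so the real data gap is adherence. None of these supplies a reference value or separates the two effects.

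**Conclusion.** The point holds in this form. The planned ratios describe risk stratification among patients who have all agreed to model-guided care. Relative to the score's advice-free performance they may be attenuated, unchanged or inflated. Under the assumed 20% and 5%, a true ratio of 4.0 could appear as 2.0, 4.0 or 6.0. A ratio near 1 cannot distinguish a weak score from effective advice concentrated in the High group. Neither the ratios nor the per-group incidences can address the third objective, so the mitigation part of the SAP's Conclusion has no planned analysis behind it.

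The algebra does not depend on the assumed figures, but the sizes do. The direction rests on how the benefit of advice is shared between groups, which the documents do not establish. Agreement to follow advice is also not proof that it was followed; if few complied, the distortion would be small, but the plan has no means of showing this.

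**What to change.** Make three wording changes in the SAP:

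1. Define the relative risk and odds ratio as estimates of stratification under model-guided care, by the risk group assigned at first assessment, before any advice. The protocol's sequence implies this timing; the SAP should fix it.
2. State that neither these ratios nor the incidences will be read as evidence that the recommendations reduced complications.
3. Remove the mitigation claim from the Conclusion, or label the third objective descriptive and hypothesis-generating.

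Where records allow, also capture whether preoperative and postoperative recommendations were followed, and report incidence by risk group and uptake as description only. This is optional.

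The wording costs nothing beyond a narrower claim for the third objective. The uptake data cost more, because Study Procedures list six kinds of recommendation. The protocol already states a mean follow-up of 15 months, and the SAP refers to a notebook with results, so some uptake data may have to be reconstructed from existing records. The wording changes do not depend on that.

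### Clinical utility is the primary aim, but the only comparative outcome formulas are the High/Low RR and OR, which ignore the share flagged and the Moderate group and cannot alone support a conclusion on prediction or utility

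*Combined protocol and SAP*

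**What the plan says.** The protocol Introduction states: "The primary aim is to evaluate the clinical utility of an AI-based risk assessment model in predicting and mitigating complications". The SAP Introduction has a close variant: "The primary aim of the study is to assess the clinical utility of an AI-based risk assessment model in identifying and mitigating risk factors". Both documents also list an objective on effects: "To assess the impact of AI-generated recommendations on surgical outcomes and complication rates". The primary outcome is "Incidence of complications within 45 days post-surgery".

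Under Statistical Methods, Outcome Analysis, the SAP gives two formulas: "Relative Risk = (Incidence in high-risk group) / (Incidence in low-risk group") and "Odds Ratio = (Odds of complications in high-risk group) / (Odds of complications in low-risk group"). The Descriptive Statistics list is looser, with "Relative risk and odds ratio for complications in each risk group". This leaves a Moderate contrast open but supplies no formula for one.

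The SAP also plans the number and percentage of patients per risk group, the incidence of complications per group, and the count and percentage of complications per group. The Pearson correlations relate the risk score to patient factors, not to complications. No sensitivity, specificity, predictive value or net benefit is named, and no interval is mentioned for any outcome statistic. Neither document describes a group treated without the recommendations, and agreement to follow them is an inclusion criterion.

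**The concern.** Whether a three-level risk classification predicts usefully depends on what it catches and what that costs: how many patients are flagged, what share of complications falls among them, and how safe the unflagged patients are. A ratio of two group-specific rates answers a narrower question, namely how different the two extreme groups are. If the report leads with a large RR, readers may take it as evidence of utility even when most complications arise in patients classed Moderate or Low. The primary aim would then have no statistic that addresses it.

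**Working it through.** The documents give no sample size, group sizes, complication rates or planned effect, so there is no figure to reproduce. Every rate and group size below is an assumption. The algebra does not depend on them.

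**Formulas.** Let each group g have n_g patients and incidence p_g.
- RR = p_H / p_L. OR = [p_H/(1 − p_H)] / [p_L/(1 − p_L)]. Neither n_g nor p_M appears.
- Sensitivity of High versus the rest = n_H·p_H / (n_H·p_H + n_M·p_M + n_L·p_L). All group sizes and all three incidences appear.

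**Step 1: vary group sizes.** Assume incidences of 20%, 8% and 4% and 1,000 patients. RR = 0.20/0.04 = 5.0 and OR = (0.20/0.80)/(0.04/0.96) = 6.0 in both tables.

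| | Groups 5/35/60% | Groups 40/40/20% |
|---|---|---|
| Complications H + M + L | 10 + 28 + 24 = 62 | 80 + 32 + 8 = 120 |
| **High versus rest** | | |
| Share flagged | 5% | 40% |
| Sensitivity | 10/62 = 16.1% | 80/120 = 66.7% |
| Specificity | 898/938 = 95.7% | 560/880 = 63.6% |
| PPV | 10/50 = 20% | 80/400 = 20% |
| NPV | 898/950 = 94.5% | 560/600 = 93.3% |
| **High + Moderate versus Low** | | |
| Share flagged | 40% | 80% |
| Sensitivity | 38/62 = 61.3% | 112/120 = 93.3% |
| Specificity | 576/938 = 61.4% | 192/880 = 21.8% |
| PPV | 38/400 = 9.5% | 112/800 = 14% |
| NPV | 576/600 = 96% | 192/200 = 96% |

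A second set of assumed incidences (20%, 8%, 5%) behaves the same way. RR is 4.00 and OR 4.75 throughout, while sensitivity of High is 10/62 = 16.1%, 40/89 = 44.9% and 80/116 = 69.0% with groups of 5/15/80, 20/30/50 and 40/20/40%.

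**Step 2: vary complications outside High** (5/35/60 table).
- Moderate complications rise from 28 to 70 of 350: RR 5.0 and OR 6.0 are unchanged; sensitivity falls from 16.1% to 10/104 = 9.6%.
- Low complications rise from 24 to 48 of 600: RR = 0.20/0.08 = 2.5 and OR = 0.25/(0.08/0.92) = 2.875. Both ratios do respond here.

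So the ratios are blind to Moderate complications, but not to a change in the Low incidence.

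**Step 3: mitigation.** If the recommendations halved risk in every group, RR = 0.10/0.02 = 5.0, unchanged, and OR = (0.10/0.90)/(0.02/0.98) = 5.44. If they halved risk only in High, RR would fall to 0.10/0.04 = 2.5, and successful advice would look like weaker prediction. Without an unadvised comparator these cases cannot be told apart from differences in underlying risk.

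**Step 4: precision.** With 62 complications among 1,000 patients (assumed), a sensitivity of 10/62 has a Wilson 95% interval of 9.0% to 27.2%. A point estimate alone would hide this.

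**The case against.** **Much of the material is already planned.** The patient percentages give the share flagged, the High incidence is the PPV of the High class, and one minus the Low incidence is the NPV of the High-plus-Moderate cut-off. The complication counts yield sensitivity, and the planned percentage may even be that share. This stands: the data are not missing, and a careful reader could do the sums. What is missing is a named measure, its interval and a statement of what the primary aim is judged on.

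**A Moderate contrast may be intended.** The descriptive line allows it. It would add another ratio of two rates, still independent of group size.

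Four stronger readings are tempting, and the documents do not support them:
- *That RR and OR ignore all complications outside High.* Step 2 shows this is untrue for Low.
- *That the SAP would base its utility conclusion on RR and OR.* It names no basis for that conclusion.
- *That a flag with a large RR is shown to be useless.* Take net benefit = TP/N − (FP/N)·t/(1 − t) with the 20/8/4% rates. At an assumed threshold t of 10%, High gives 5.6 and 44.4 per 1,000 in the two tables, against −42.2 and 22.2 for flagging everyone, so it beats both defaults. At 5% in the 40/40/20 table, High (63.2) falls below flagging everyone (73.7), but High plus Moderate gives 0.112 − 0.688/19 = 75.8 per 1,000 and exceeds it.
- *That net benefit should settle the utility question.* The protocol's Study Procedures tie recommendations to individual factors such as BMI, smoking and blood pressure, not to risk class, so advising High patients only is not the policy under study. All participants agree to follow the advice, so an averted complication in a High patient counts as a false positive. The thresholds have no source in the documents.

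**Conclusion.** The point holds in limited form. Clinical utility is the stated primary aim, and the only comparative outcome formulas are the High/Low RR and OR. At given incidences these do not depend on the share flagged, and they omit the Moderate group. Alone they cannot support a conclusion on predictive effectiveness or utility. Under the assumed rates, one RR of 5.0 is compatible with the High class capturing anywhere from 16% to 67% of complications. The size of the gap in the real data is unknown because the documents give no rates or group sizes.

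This is a gap in what the SAP derives and reports, not in what it collects, and it can be closed cheaply for prediction. It cannot be closed for mitigation by any reanalysis of this table, because there is no unadvised comparator.

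**What to change.** In SAP Outcome Analysis, add the following from the cross-table of risk group by 45-day complication, using all three groups:

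1. For High versus the rest, and for High plus Moderate versus Low: share flagged, sensitivity, specificity, PPV and NPV, each with a 95% interval.
2. Optionally, as an exploratory analysis, net benefit over a stated range of thresholds against flagging all and flagging none, with the reason for the range.
3. Three statements on interpretation. RR and OR alone do not establish utility. All these measures describe prediction in patients who agreed to follow the recommendations, so averted events appear as false positives. Without an unadvised comparator, no conclusion on mitigation follows.

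The SAP's Data Analysis section says that a notebook with code and results is already available. If outcomes had been seen before this change, label the additions post hoc.

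Cost: SAP wording and a few lines of code on data already planned. The downside is slightly more analysis, and a conclusion that may look less favourable than the RR alone.
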